5.1 Sipuleucel-T

Sipuleucel-T will be administered per standard of care in this study at either the study center or by the local referring physician. The information in this section is provided for reasons of continuity and only serves as standard of care guidelines.

5.1.1 Leukapheresis and Product Manufacturing

Patients will undergo leukapheresis at weeks 0, 2, and 4 with sipuleucel-T infused 3 days later (i.e. Monday/Thursday; Tuesday/Friday); however the 3rd infusion must be done on a schedule that allows a clinic visit at the study center the following day.

Leukapheresis will be performed at the American Red Cross who will ship the cells to the facility where sipuleucel-T is manufactured. The cell product will then be shipped to the clinical center for infusion. Since the product is shipped from the manufacturer prior to completion of quality control (QC) testing, **the cell product must not be infused until the Cell Product Disposition Form has been received by the clinical center and is marked “Approved.”**

If a cell product does not meet Dendreon quality specifications, the center will be contacted by telephone and the Cell Product Disposition Form indicating that the product is not approved will be faxed to the center. Dendreon will provide instructions for the return or destruction of cell products that are not approved. Refer to section 5.1.3 regarding repeat leukapheresis procedures.

Note that if the leukapheresis appointment is delayed or rescheduled for any reason, the physical exam must also be rescheduled for completion within the 7 days preceding the leukapheresis procedure.

5.1.2 Sipuleucel-T Administration

Approximately 30 minutes prior to infusion, patients must be pre-medicated with acetaminophen (650 mg) and diphenhydramine (50 mg).

Infusion of sipuleucel-T must begin prior to the labeled expiration time. Sipuleucel-T must be maintained in its refrigerated shipping package or stored at 2 to 8°C until the cells are infused.

Sipuleucel-T must be administered over approximately 60 minutes through a large bore IV line suitable for blood transfusion. **DO NOT USE A FILTER.** Start and stop times of the product infusion will be recorded.

Common treatment-emergent AEs such as pyrexia and/or rigors may warrant reduction of the infusion rate. If such adverse reactions occur, subsequent infusions should be administered over the shortest period that is well tolerated, but not less than 60 minutes. Patients must be observed for at least 30 minutes after the infusion.

5.1.3 Sipuleucel-T Product Release Failure

In the event that a patient's leukapheresis procedure fails or the cell product does not meet quality specifications, the patient may undergo a repeat leukapheresis procedure. There is a small possibility that a patient's cell product will fail to meet quality requirements more than once. In such instances, the patient may not receive all 3 infusions.

In rare instances, it may be determined that it is not possible to make the investigational product from a patient's leukapheresis product that will pass the quality specifications, and he will not be able to receive any infusions of sipuleucel-T after multiple failed attempts.

Patients receiving fewer than 3 doses of sipuleucel-T will not continue on study and receive indoximod/placebo.

5.2 Indoximod/Placebo

The day after the 3rd and final sipuleucel-T infusion, the patient will begin indoximod 2400 mg/day or an identical appearing placebo. The study drug will be continued twice daily, approximately 12 hours apart for 6 months. The capsules should be taken with water on an empty stomach one hour before breakfast and one hour before dinner. Antacids are to be avoided.

The patient will be provided with a daily medication log to record times of administration, side effects, and missed doses, if any, through week 14 (immune monitoring endpoint). After week 14, the patient will be asked to record only events such as missed doses or side effects, rather than keeping a daily medication log.

The patient will be instructed to bring the medication log and study drug bottles (including any empties) to each appointment for reconciliation.

5.2.1 Expected Side Effects

All of the subjects in the indoximod clinical trials had at least one adverse event. The most frequently reported adverse events (regardless of attribution), occurring in $\geq 20\%$ of patients were fatigue, nausea, headache, and alopecia. The most frequently reported laboratory abnormalities (regardless of attribution), occurring in $\geq 20\%$ of patients were lymphopenia, anemia and hyperglycemia.

The most frequently observed adverse event which is possibly related to indoximod is fatigue (12%). Lymphopenia (16%) is the most frequently observed laboratory abnormality possibly related to

indoximod. The collective safety data from the clinical studies so far indicates indoximod has an acceptable safety profile and is safe for the treatment of patients with solid tumors.

Toxicities as updated with version 6 of the indoximod investigator's brochure (February 2015) are as follows:

Likely: Likely to happen to 20% or more of patients

- Fatigue or feeling tired
- Nausea
- Anorexia or loss of appetite
- Decrease in red blood cells (anemia)
- Diarrhea

Less Likely: Likely to happen to 10 to 19% of patients

- Decrease in white blood cells (neutrophils and lymphocytes)
- Abdominal pain
- Feeling short of breath or breathless (dyspnea)
- Rash
- Vomiting
- Constipation
- Decrease in platelets
- Headache
- Hair loss

Rare: Likely to happen to 1% than 10% of patients

- Dizziness
- Fever associated with low white blood cells
- Lung infection
- Increase in blood potassium, glucose, and creatinine levels
- Sleeplessness (insomnia)
- Low blood levels of sodium
- Multi-organ failure
- Low blood pressure
- Dehydration
- Ringing in ears
- Fever associated with low white blood cells (febrile neutropenia)
- Mouth Sores (Oral mucositis)
- Decrease in white blood cells

This drug is being employed in human clinical trials for solid tumors, breast cancer, melanoma, and pancreatic cancer. The profile of adverse events appears similar to that predicted for the study

subjects enrolled in these studies, e.g., a patient population with life-threatening disease. (7).

The data obtained from the Phase 1 studies performed under IND78060 suggest that certain patients with a history of exposure to targeted biologics involving components of the IDO pathway may be adversely impacted following administration of indoximod. However, these same patients were observed to have a clinical response after management of the toxicity. Therefore, the combination of indoximod with biologic agents including ipilimumab is being carefully evaluated in the clinical trial setting as described above.

The drug has not shown evidence of significant drug interactions. It is now being systematically tested in combination with docetaxel for metastatic breast cancer, in combination with ipilimumab for metastatic melanoma, in combination with temozolomide for glioblastoma, and in combination with gemcitabine/nabpaclitaxel for metastatic pancreas cancer in clinical trials under IND78189 and IND120813.

Based on phase I testing no serious toxicity is anticipated. Therefore, no specific supportive care measures are expected to be required for the drug administration itself; however dose withholding will occur for Grade 3 and 4 treatment related toxicity per section 5.2.3. Unexpected adverse events will be treated as medically indicated by the involved physicians.

Specific attention to development of autoimmune events or activation of latent infections will be given as trials using other immune-modulatory agents such as CTLA-4 blocking antibodies have shown a correlation between disease responses and so called autoimmune breakthrough events (ABEs) like hypophysitis, colitis, autoimmune hepatitis, or dermatitis. It is for this reason that they are distinguished from other adverse events. When used immediately post sipuleucel-T as in this clinical trial, it might increase the side effects of cytokine release from last infusion of sipuleucel-T. Refer to section 6.2 for study specific monitoring. Section 5.2.2 provides management of selected events.

Placebo

Placebo is a look-alike capsule containing no active ingredients and therefore no serious side effects are expected.

5.2.2 Management of Selected Events During Indoximod/Placebo

Autoimmune Events

Patients will be evaluated for autoimmune events by a checklist provided in Appendix IV every 2 to 8 weeks according to the schedule in section 6.2. This checklist, in addition to serologic tests, will be used by the study physicians to determine if further evaluation for autoimmune disease is warranted by an appropriate specialist in the organ system affected. This will be done to avoid misinterpretation of spurious autoimmune test results.

Treatment with indoximod can be withheld for up to four weeks while the appropriate workup/supportive care is performed and a determination made by the primary investigator whether the patient can remain on trial or should discontinue treatment.

Resuming treatment with indoximod after the autoimmune event has resolved or is stable in a patient who demonstrated an objective disease response may be entertained on a case by case basis if the principal investigator ([name]), the treating investigator, and the patient agree to do so.

Toxoplasma Serology

There is some data supporting the role of Indoleamine 2,3-dioxygenase (IDO) in the suppression of latent chronic infections. New headaches, mental status changes, neurological deficits, or visual changes should be evaluated immediately for possible CNS or ocular toxoplasmosis reactivation and evaluated/treated as needed.

All patients will be screened at study entry for toxoplasma.

Toxoplasma serology positive patients who do not have a sulfa allergy will be offered prophylaxis with Septra DS one tablet daily on Monday, Wednesday, and Friday. Toxoplasma serology positive patients with a sulfa allergy who still want to enroll will be allowed to use atovaquone 750 mg twice daily administered with meals. Patients who cannot tolerate or choose not to take prophylaxis will not be excluded from the study, but they should do so only after clear informed consent has been obtained about the possible risks of toxoplasma reactivation.

Toxoplasma serology negative patients should be counseled on avoiding exposure to toxoplasma by avoiding direct skin contact with soil, cat feces, and raw meats. Domestic cats should be kept indoors and be fed pet food to prevent ingestion of contaminated soil or meat. Patients should thoroughly wash their hands after encountering any of these sources prior to eating or food

preparation. All utensils and surfaces that come into contact with raw meats should not touch cooked or prepared food without being washed first. Produce should be washed well prior to eating. Meats should be cooked completely until they are not pink and their juices run clear.

Toxoplasmosis IgM and IgG titers will be checked at baseline and rechecked at the final treatment visit for serology negative patients. In addition, IgM anti toxoplasma titers will be checked if acute infection in serology negative patients is suspected while on study.

Proteinuria

Urine analysis will be performed every 2 weeks for 6 weeks then every 4 to 8 weeks thereafter. Any protein $\geq 2+$ on dipstick or new urine active sediment/ eosinophils should be evaluated.

Positive ANA Panel or Symptoms of an Autoimmune Condition

ANA will be drawn every four weeks. Any positive panel (> 5 times the upper limit of normal) should reflex over to a titer panel to determine the specific type. Any antibody titer > 5 times the ULN with symptoms consistent with an autoimmune condition should prompt withholding of indoximod and a rheumatologic evaluation. Also if inflammatory arthritis develops CCP and RF antibody titers will be evaluated.

TSH > 5

TSH will be monitored every 4 to 8 weeks and if it increases above a TSH of 5 a workup for autoimmune thyroiditis will be performed (anti-TG and anti-TPO Ab tests, thyroid uptake scan, FNA of the thyroid if warranted).

Also baseline and every 4 to 8 weeks, LH, FSH, ACTH, cortisol will be used to monitor for hypophysitis. These labs should be drawn between 7-8 AM due to the natural circadian variation of ACTH and cortisol. If any of these tests are lower than the reference lab values at the clinical institution and the primary investigator suspects hypopituitarism then study treatment should be held and a workup performed. This includes an MRI of the brain with attention to the sellar area to evaluate for hypophysitis.

Ophthalmologic Complaints

Any ophthalmologic complaints (including new ocular pain/inflammation, photosensitivity, or diminished vision) will be evaluated by an ophthalmologist if the treating investigator deems it necessary.

Symptoms of Myositis

CPK will be checked if any symptoms of myositis occur.

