5.2.3 Indoximod /Placebo Dose Modifications (toxicity related)

Should a patient experience a Grade 3 toxicity that is possibly, probably, or definitely related to the study drug as determined by the treating investigator, the study drug will be held.

- If the toxicity resolves to Grade 2 or less within 7 days, the study drug may be resumed. If the toxicity recurs the event will count toward the early study stopping rule for excessive toxicity (section 12.2).
- If the toxicity does not improve to a grade 2 or less within 7 days or recurs, the patient will be permanently discontinued from treatment and the event will count toward the early study stopping rule for excessive toxicity (section 12.2).

If the patient experiences any Grade 4 toxicity, the study drug will be stopped and the event will count toward the early study stopping rule for excessive toxicity (section 12.2). If all toxicities resolved to Grade 2 or less, resumption of the study drug may be considered but must be discussed and agreed to by the investigator and Principal Investigator ([name]).

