5.4 Duration of Indoximod/Placebo

Indoximod/placebo will continue twice daily for 24 weeks unless any one of the following occurs:

- Treatment related toxicity results in a discontinuation of indoximod /placebo for more than 7 days or a toxicity recurs despite delay
- indoximod/placebo is discontinued for more than 4 weeks for any reason
- The patient is non-compliant or withdraws consent

- Disease progression occurs, although the intent is to treat all patients for a minimum of 12 weeks with indoximod/placebo before declaring progression. In addition, treatment will not be discontinued solely based on early PSA progression in the absence of clinical or definite radiologic progression.
- Inter-current illness interferes with study drug administration
- Unacceptable adverse events
- The treating investigator or Principal Investigator feels the patient's continuing participation is not in the best interest of the patient

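### Sections 5.2.2, 5.2.3 and 5.4 give incompatible stop-or-continue instructions for two kinds of treatment-related event that keep a patient off study drug for more than 7 days

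*Combined protocol and SAP*

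**What the plan says.** Three sections of the protocol govern interruption of study drug.

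- **Section 5.2.2, autoimmune events.** The hold is described as follows: "Treatment with indoximod can be withheld for up to four weeks while the appropriate workup/supportive care is performed". It is not limited by grade or attribution. After the work-up, the investigator decides whether the patient stays on the trial. On restarting: "Resuming treatment with indoximod after the autoimmune event has resolved or is stable in a patient who demonstrated an objective disease response may be entertained". That is decided patient by patient, and the principal investigator, the treating investigator and the patient must all agree.
- **Section 5.2.3, related Grade 3 toxicity.** Study drug is held. Then: "If the toxicity does not improve to a grade 2 or less within 7 days or recurs, the patient will be permanently discontinued from treatment".
- **Section 5.2.3, Grade 4 toxicity.** Study drug is stopped. Then: "If all toxicities resolved to Grade 2 or less, resumption of the study drug may be considered". The investigator and the Principal Investigator must agree. No time limit is given.
- **Section 5.4, end of treatment.** Any one of several listed events ends study drug. One is "Treatment related toxicity results in a discontinuation of indoximod /placebo for more than 7 days or a toxicity recurs despite delay". Another is "indoximod/placebo is discontinued for more than 4 weeks for any reason".

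Section 5.2.1 sets autoimmune events apart because other immune-modulating agents have shown a link between such events and response: "It is for this reason that they are distinguished from other adverse events". It also sends related Grade 3 and 4 toxicity to Section 5.2.3 for withholding, without excepting autoimmune events.

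**The concern.** Two time limits, 7 days and four weeks, can apply to the same patient, and nothing says which takes precedence. The resumption standards also differ: Section 5.2.2 accepts an autoimmune event that is merely stable, while Section 5.2.3 works to Grade 2 or less.

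Autoimmune events are the class that the protocol singles out for specific attention, and up to 5 sites must apply these rules. Two things are at stake. One is safety, because the same patient may be restarted under one section and must be taken off drug under another. The other is exposure: study drug starts in week 4 and the primary ELISPOT sample is taken at week 14, so an interruption in that interval falls on the exposure that the primary comparison is meant to test.

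**Working it through.** The plan states no figure for this point, so the check sets the rules side by side.

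**Inputs.** Section 5.2.2: hold of up to 4 weeks = 4 × 7 = 28 days. Section 5.2.3: 7 days to reach Grade 2 or less for related Grade 3; no limit for Grade 4. Section 5.4: more than 7 days off drug if treatment related; more than 28 days otherwise. The range in which Section 5.2.2 permits a hold and the 7-day criterion is met is therefore days 8 to 28.

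| Situation | 5.2.2 | 5.2.3 | 5.4 | Result |
|---|---|---|---|---|
| Related autoimmune event, Grade 1–2, off drug 8–28 days | Hold permitted | Not addressed | Stop | Conflict |
| Related autoimmune event, Grade 3, improved by day 7, hold continued for work-up to day 8–28 | Hold permitted | Drug may be resumed | Stop | Conflict |
| Related autoimmune event, Grade 3, not improved by day 7 | Hold permitted to day 28 | Permanent stop | Stop once past day 7 | Conflict |
| Related Grade 4 event, Grade 2 or less only after day 7 | Applies only if autoimmune | Resumption may be considered | Stop | Conflict |
| Other related Grade 3 event, not improved by day 7 | Does not apply | Permanent stop | Stop once past day 7 | Agree |
| Autoimmune work-up, not treatment related, off drug up to 28 days | Hold permitted | Does not apply below Grade 4 | Criterion not met | Agree |

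The first three rows are one situation, a treatment-related autoimmune hold past day 7. The fourth row is the second situation.

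**Exposure in one affected patient.** The primary sample falls 10 weeks after study drug starts. Suppose drug is held t weeks after the first dose. If it is resumed after h weeks, the patient has 10 − h weeks on drug by week 14. If it is never resumed, he has t weeks. The difference is 10 − h − t, or zero if t + h is 10 or more.

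- With h = 4, the difference is 6 − t, so at most 6 weeks.
- With h just over 1 week, it is 9 − t, so just under 9 weeks at most.

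The documents do not give t, h or the number of such patients. These are limits for one patient and assume that drug is in fact resumed before week 14.

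**Link to the stopping rule.** Section 12.2 and the footnote in Section 8.2 count a related Grade 3 event that has not resolved to Grade 2 or better in 7 days, and any Grade 4 or 5 event.

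- The unresolved Grade 3 autoimmune event counts whether drug is held for 7 days or for 28.
- The Grade 4 event counts whether or not drug is resumed.
- A Grade 1–2 autoimmune event held past day 7 does not count under either limit.

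Hold length is not an input, so the conflict changes none of these counts.

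**The case against.** **Section 5.2.2 may be an intended exception.** Section 5.2.1 does treat autoimmune events as a class apart, and a four-week allowance for specialist work-up reads naturally as a special rule. This is plausible but unwritten. No sentence exempts these events from Section 5.2.3 or 5.4, and Section 5.2.1 itself routes related Grade 3 and 4 toxicity to Section 5.2.3.

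**The sections can be read as layered.** Section 5.2.2 is permissive, so its four weeks could be a ceiling that applies only where Section 5.4 has not already ended treatment. Likewise, Section 5.2.3 may be silent on time for Grade 4 because Section 5.4 supplies the limit. That is also possible. It is the opposite of the exception reading for autoimmune events, and the text does not choose between the two.

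**Resumption is restricted.** This stands in part. Under Section 5.2.2 it concerns objective responders only, and both resumption routes need the Principal Investigator's agreement, which reduces divergence between sites. The first scheduled on-treatment scans are at week 14, so a scan-based response would rarely be on record before the primary sample. But agreement to resume does not remove the stop criterion in Section 5.4.

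**Such events may be rare.** Section 5.2.1 anticipates no serious toxicity, and Section 2.3 reports two mild hypophysitis cases that resolved without drug treatment. This stands as a limit on how much can be claimed.

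**Two stronger readings do not hold.** A reader might infer that the conflict changes which patients count toward the 5 events that stop the trial. It does not, because Sections 8.2 and 12.2 do not use hold length. Section 5.2.3 does count recurrences that those two sections do not mention, but that is a separate discrepancy. A reader might also take 4/10 = 40% of pre-endpoint exposure as the size of the problem. That is the most that one patient could lose to a single four-week hold under Section 5.2.2 alone. He is off drug in those weeks under the competing rules too, so it does not measure the difference between them.

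**Conclusion.** The contradiction is real and confined to two situations: a treatment-related autoimmune event with drug held for 8 to 28 days, and a treatment-related Grade 4 event that reaches Grade 2 or less only after day 7. In each, one section permits or allows for continuation and another ends treatment. For other related Grade 3 toxicity, and for autoimmune holds of up to four weeks that are not treatment related, the sections are consistent.

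The conclusion rests on the text as written, with no implied exception and no implied order of precedence. Its practical size is unknown, because the documents give no rate for such holds. An effect on the primary comparison is possible but not shown. The point should still be corrected, because the instructions for an affected patient are opposite and the correction is inexpensive.

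**What to change.** Reconcile the passages so that Sections 5.2.2, 5.2.3 and 5.4 give one consistent instruction on holding, discontinuing and resuming study drug in these two situations. State explicitly:

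- whether treatment-related autoimmune events are an exception to the 7-day criterion in Section 5.4 and, where they are Grade 3, to the 7-day rule in Section 5.2.3;
- whether Grade 4 events are an exception to the 7-day criterion in Section 5.4;
- which resumption standard applies to an autoimmune event that falls under both Section 5.2.2 and Section 5.2.3.

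The sponsor and investigators choose the rule; this review takes no view on which is right. The cost is protocol amendment wording. This point requires no change to the sample size, the primary analysis or the Section 12.2 boundary.

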5.5 Duration of Study Participation

Patients who begin indoximod/placebo will be followed for disease response until progression and then survival only for 2 years from study enrollment.

6 Clinical Evaluations and Procedures

Scheduled evaluations may be performed +/-3 days from the targeted date to allow for holidays and other scheduling conflicts. The final post treatment visit may be performed +/- 2 weeks. Follow-up visits may be performed +/- 4 weeks. In addition, targeted days may be altered as clinically appropriate.

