6.1 Baseline and Post Treatment

Study	baseline	Weeks 0-28	Post rx visit	F/U
Evaluation	Prior to 1 st leukapheresis	Refer to table in 6.2	4 weeks after last dose of indoximod /placebo	Every 3 months from post-rx visit until 2 years from enrollment ⁸
Consent	X			
Medical history	X			
Physical exam	X			
Assessment of symptoms and analgesic needs	X		X	X
Weight	X		X	
Vital signs	X		X	
ECOG PS	X		X	
CBC/diff/plt, CD4 count	X		X	
Bun/creatinine, Na, K, Ca, Mg, tot. bili, AST, ALT, alkaline phosphatase, LDH, albumin, total protein	X		X	
Circulating Tumor Cells (CTCs)	X			
PT/INR, CPK	X			
Urinalysis ¹	X			
Testosterone	X		X	
HIV 1 & 2, hepatitis B, Hepatitis C, HTLV-1	X			
β-HCG	X			
ESR	X			
EKG	X			
CT of chest, abd, pelvis	X			X
Bone scan	X			X
PSA	X			X
Research Related				
FACT-P questionnaire	X		X	
TSH, Free T4, LH, FSH, ACTH, Cortisol ⁴	X			
Toxoplasma Ab titer	X		X ⁵	
Rheumatoid Factor	X			
C-Reactive Protein	X			
ANA panel ³ and auto-immune symptom checklist (app IV)	X			
C3, C4, CH50	X			
Samples for immune monitoring, K/T ratio and indoximod level (9 – 10 ml green tops, 1-10 ml red top)	X, X ⁶			
immune response biomarker (1-10 ml red top)	X			
Optional bx ⁷	X			

- 1- Proteinuria – any protein ≥ 2+ on dipstick or new urine active sediment/EOS should be evaluated per section 5.2.2
- 2- Toxoplasma serology positive patients will be offered prophylaxis with Septra DS per section 5.2.2
- 3- Refer to section 5.2.2 for positive ANA panel or symptoms of an autoimmune condition
- 4- Refer to section 5.2.2 for TSH > 5 or evidence of hypopituitarism
- 5- Retest sero-negative patients per section 5.2.2
- 6- Two separate sets of baseline samples to be done (i.e. at screening and prior to 1st sipuleucel-T infusion)
- 7- Biopsy for immune response biomarker only for those who provided additional consent within the treatment consent
- 8- Once disease progression is confirmed follow for survival status only

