6.2 During Treatment

Treatment	Week	Standard of Care			Research funded lab work to be performed by local (institutional) lab	Research Related Samples	indoximod / placebo count
Leukapheresis followed by sipuleucel-T infusion	0						
	1						
Leukapheresis followed by sipuleucel-T infusion	2						
	3						
Leukapheresis followed by sipuleucel-T infusion, start indoximod /placebo day after infusion	4	Prior to indoximod /placebo Physical exam, FACT-P				9 – 10 cc green, 1 – 10 cc red (pre indoximod/ placebo)	
indoximod /placebo twice daily continuously for 6 months	5						
	6	PE, review of side effects		CBC/diff/plt, chem ¹ , U/A ²	Thyroid function, C-reactive protein, ANA panel, Auto-immune symptom list	9 – 10 cc green, 1 – 10 cc red	Reconcile Drug
	7						
	8	PE, review of side effects, FACT-P	PSA	CBC/diff/plt, chem ¹ , U/A ²	Thyroid function, C-reactive protein, ANA panel, Auto-immune symptom list		Reconcile Drug
	9						
	10	PE, review of side effects		CBC/diff/plt, chem ¹ , U/A ²	Thyroid function, C-reactive protein, ANA panel, Auto-immune symptom list	9 – 10 cc green, 1 – 10 cc red	Reconcile Drug
	11-13						
	14	PE, review of side effects, FACT-P	PSA, CT of chest, abd, pelvis, bone scan	CBC/diff/plt, chem ¹ , CTCs ³ , U/A ²	Thyroid function, C-reactive protein, ANA panel, Auto-immune symptom list	9 – 10 cc green, 2 – 10 cc red, opt biopsy	Reconcile Drug
	15-19						
	20	PE, review of side effects, FACT-P	PSA	CBC/diff/plt, chem ¹ , U/A ²	Thyroid function, C-reactive protein, ANA panel, Auto-immune symptom list		Reconcile Drug
	21-23						
	24	PE, review of side effects		CBC/diff/plt, chem ¹ , protein, U/A ²			Reconcile Drug
	25-27						
28	PE, review of side effects, FACT-P	PSA, CT of chest, abd, pelvis, bone scan,	CBC/diff/plt, chem ¹ , U/A ²	Thyroid function, C-reactive protein, ANA panel, Auto-immune symptom list	9 – 10 cc green, 1 – 10 cc red	Final Reconcile Drug	

1- chem to include Bun/creatinine, Na, K, Ca, Mg, tot. bili, AST, ALT, alkaline phosphatase, LDH, albumin, total protein

2- Proteinuria – any protein ≥ 2+ on dipstick or new urine active sediment/EOS should be evaluated per section 5.2.2

3- CTCs - circulating tumor cells

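### Table 6.2 omits, at all seven on-treatment visits, the LH, FSH, ACTH and cortisol draws that section 5.2.2 requires every 4 to 8 weeks

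*Combined protocol and SAP*

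**What the plan says.** Section 5.2.2 gives the requirement: "Also baseline and every 4 to 8 weeks, LH, FSH, ACTH, cortisol will be used to monitor for hypophysitis". It fixes the draw time at 7 to 8 AM. If a value is below the local reference range and hypopituitarism is suspected, study drug is to be held and a workup done that includes a brain MRI.

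Section 5.2.1 directs the reader to section 6.2 for the study's monitoring and to section 5.2.2 for managing events.

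Table 6.1 has a row "TSH, Free T4, LH, FSH, ACTH, Cortisol", marked only in the baseline column, which is timed "Prior to 1 st leukapheresis". For weeks 0-28 the table says "Refer to table in 6.2". Footnote 4, attached to the hormone row, reads "Refer to section 5.2.2 for TSH > 5 or evidence of hypopituitarism".

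Table 6.2 has a column for research-funded local labs. At weeks 6, 8, 10, 14, 20 and 28 that column reads "Thyroid function, C-reactive protein, ANA panel, Auto-immune symptom list". At week 24 the thyroid, C-reactive protein, ANA and symptom-list entry is absent. The chemistry footnote reads "chem to include Bun/creatinine, Na, K, Ca, Mg, tot. bili, AST, ALT, alkaline phosphatase, LDH, albumin, total protein".

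**The concern.** The narrative section requires a repeated safety test, and the visit table that sites use to order tests does not contain it. A coordinator who builds orders from table 6.2 would draw the hormones at baseline and never again on a schedule. The hold-and-MRI rule in 5.2.2 starts from a low hormone value. Without scheduled draws it would operate only when someone already suspected a problem and ordered the test. With up to five sites, different sites could also follow different texts.

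The protocol treats this risk as worth watching. Section 2.3 reports two mild cases of hypophysitis in the higher dose cohorts, and section 5.2.1 lists hypophysitis among the autoimmune events that need particular attention.

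**Working it through.** The plan states no figure to reproduce. The check is a reading of table 6.2 against 5.2.2, followed by interval arithmetic for a workable schedule.

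**1. Count of visits.** On-treatment visits are those in table 6.2 after study drug starts in week 4.

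| Week | Thyroid function listed | LH, FSH, ACTH, cortisol listed |
|---|---|---|
| 6 | yes | no |
| 8 | yes | no |
| 10 | yes | no |
| 14 | yes | no |
| 20 | yes | no |
| 24 | no | no |
| 28 | yes | no |
| Total | 6 of 7 | 0 of 7 |

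**2. Other places that might supply the draws.**
- The chemistry footnote names its analytes, and none is a pituitary or adrenal hormone.
- Section 6.2.1 covers immune assays, kynurenine/tryptophan, indoximod levels and biomarkers.
- The week 4 pre-drug visit lists no hormones.
- Table 6.1 marks them at neither the post-treatment visit nor follow-up.
- Footnote 4 of table 6.1 points to 5.2.2 but names no visit.

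**3. Neighbouring 5.2.2 rules.** Urinalysis is to be done every 2 weeks for 6 weeks, then every 4 to 8 weeks. Table 6.2 has it at weeks 6, 8, 10, 14, 20, 24 and 28, which fits. TSH is to be done every 4 to 8 weeks. The widest gap between thyroid draws is 28 − 20 = 8 weeks, which is within the limit. The pituitary hormones are the only one of these three items absent altogether, which looks like an oversight.

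**4. Do existing visits allow a compliant schedule?** Section 5.2.2 does not say whether the first interval runs from drug start or from the baseline draw, so both are checked.

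- *From drug start (week 4)*, with draws at weeks 8, 14, 20 and 28: 8 − 4 = 4; 14 − 8 = 6; 20 − 14 = 6; 28 − 20 = 8. All lie within 4 to 8 weeks.
- *From baseline*, let B be the weeks from the baseline draw to week 0. No hormone window is given beyond the draw preceding first leukapheresis, so B = 0 to 4 is an assumed range. Without a week 4 draw, the gap to week 8 is 8 + B, which meets the limit only at B = 0. With a week 4 pre-drug draw, the first gap is 4 + B, that is 4, 5, 6, 7 or 8 weeks for B = 0, 1, 2, 3 or 4. The later gaps are again 4, 6, 6 and 8. Every gap is within 4 to 8 weeks.

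**5. Volume.** With about 50 patients (synopsis), all completing treatment: 4 × 50 = 200 panels, or 5 × 50 = 250 with the week 4 draw.

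**6. ANA, a separate minor mismatch.** Section 5.2.2 calls for ANA every four weeks. Table 6.2 has it at weeks 6, 8, 10, 14, 20 and 28, with gaps of 2, 2, 4, 6 and 8 weeks. Two of the five gaps exceed four weeks.

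**The case against.** The best case against the point is that table 6.2 is silent and does not countermand 5.2.2. Section 5.2.1 and footnote 4 of table 6.1 both send sites to 5.2.2, which remains in force. This stands: a reader might infer that the two sections give opposing instructions, but the documents show only that the visit table leaves out something the text requires.

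A second argument is that thyroid function in table 6.2 is shorthand for the whole table 6.1 hormone row, since 5.2.2 puts all these tests under one heading with one interval. The documents do not say so, and LH, FSH, ACTH and cortisol are not thyroid function tests. A site should not have to guess this.

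Third, the practical risk is limited, and this also stands:
- The two reported cases were mild and resolved without drug treatment.
- Twelve patients at 1200 mg twice daily or higher had no notable toxicity.
- The February 2015 toxicity list, which extends to events at 1%, does not name hypophysitis.
- Sodium, thyroid function and the Appendix IV checklist are still followed.
- The hold rule needs investigator suspicion as well as a low value.
- The patient calendars in OnCore (section 10.1) are not in these documents and may already carry the tests.

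How to read LH and FSH in men with castrate testosterone (section 3.4) is a question for 5.2.2. It does not bear on whether the visit table should match it.

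**Conclusion.** The point holds as an omission from the visit schedule: 0 of 7 on-treatment visits carry the four hormones that 5.2.2 requires every 4 to 8 weeks. It should be corrected because sites are pointed to table 6.2 for monitoring and the missing tests feed a treatment-hold rule. The baseline part of the requirement is met by table 6.1.

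The consequence is confined to safety monitoring. A reader might infer that patients went unmonitored or that the trial's results are affected. Neither follows: no missed draw is shown, 5.2.2 still binds sites, and no endpoint or analysis uses these hormones.

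A reader might also infer that the baseline hormones must be drawn within two weeks of first leukapheresis, because a first on-treatment draw at week 6 is 6 + B weeks from baseline and exceeds 8 when B is above 2. That rests on counting the interval from baseline, which 5.2.2 does not specify, and it overlooks the week 4 visit. No new baseline window is needed.

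The visit count needs no assumption. The proposed schedule rests on nominal weeks and, under the baseline reading, on B between 0 and 4.

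**What to change.** Add to the research-funded lab column of table 6.2 an entry for LH, FSH, ACTH and cortisol, with a note to draw at 7-8 AM and a cross-reference to 5.2.2. Weeks 8, 14, 20 and 28 are suitable. If the sponsor intends the interval to run from the baseline draw, add the same entry at the existing week 4 pre-drug visit. Check that the OnCore calendars agree. If the sponsor intended baseline testing only, it should amend 5.2.2 instead, so that the two texts match.

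No extra statement about visit windows is needed, because the opening of section 6 already works from target dates: "Scheduled evaluations may be performed +/-3 days from the targeted date to allow for holidays and other scheduling conflicts".

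The cost is four panels per patient, or five with the week 4 draw, and early-morning attendance at those visits. Section 5.2.2 already imposes the tests and the draw time, and no new visits are created.

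Separately, as a minor edit, reconcile the ANA frequency between 5.2.2 and table 6.2.
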